3.8.2. Efficacy Analysis

The following endpoints will be used to evaluate durability of treatment effect:

- Change from baseline in PANSS total score, and subscales (positive, negative, and general psychopathology subscales) by visit
- Change from baseline in CGI-S by visit
- Shift analysis in CGI-S
- Time to treatment discontinuation

Summary statistics will be provided for all continuous endpoints based on observed data.

Change from current (A304) and precedent (A303) study baseline in PANSS total score and subscales will be summarized for the subset of subjects who participated in the patient voice substudy.

CGI-S response will be categorized into the categories summarized in [Table 1](#). The number and percentage of subjects in each category and with shifts from baseline will be summarized based on the observed data by descriptive statistics at 4, 12, 24 and 52 weeks. The shift categories are summarized in [Table 2](#).

Time to treatment discontinuation will be analyzed using the Kaplan-Meier method. Both all-cause discontinuation and discontinuation due to AE will be summarized. For prematurely discontinued subjects (all-cause or due to AE), time to discontinuation is defined as time from the date of first dose of study drug to the date of last dose of study drug. Other subjects will be censored at the last dose of the study drug.

Table 1: Definition of CGI-S Categories

Response Category	CGI-S Score
Markedly to Extremely Ill	≥ 5

Response Category	CGI-S Score
Moderately Ill	4
Normal to Mildly Ill	≤3

Table 2: Shift Categories for CGI-S response

Shift from Baseline Category for CGI-S Response	
Baseline Category	Shift Category
Markedly to Extremely Ill	No change ≥1 level improvement 2 level improvement
Moderately Ill	No change 1 level improvement 1 level worsening
Normal to Mildly Ill	No change ≥1 level worsening 2 level worsening

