7.3. Subject Withdrawal

A subject may be discontinued from the study at any time if the subject, investigator, or the sponsor determines that it is not in the best interest of the subject to continue participation. If a subject has an absolute neutrophil count (ANC) $< 1.0 \times 10^3$ per μL or glycosylated hemoglobin (HbA1c) $\geq 6.5\%$ at any time during this extension study, the subject will be discontinued from the study. Other reasons for discontinuation include the following:

- Adverse Event (AE)
- Lack of Efficacy
- Lost to follow-up
- Withdrawal by subject
- Protocol Deviation (non-compliance with study drug or study procedures)
- Pregnancy
- Study terminated by sponsor
- Other

If a subject withdraws from the study for any reason, he or she will be asked to return to the clinic for an early termination (ET) visit. The ET visit should be scheduled as close as possible to the subject's last dose and will mimic the assessments scheduled to be conducted at the end of treatment (EOT) visit (Visit 27, [Table 3](#)). Following the ET visit, subjects who discontinue study drug but are willing to come in for further assessments will be asked to complete 2 safety follow-up visits 2 and 4 weeks after the ET visit (same assessments as Visits 28 and 29 in [Table 3](#)). They will then be asked to return to the study center for monthly visits according to the schedule outlined in [Table 3](#) for follow-up weight assessments, adverse events, and documentation of any new antipsychotic medications the subject is taking.

Following ET, any ongoing AEs will be followed until resolution, or until deemed stable by the investigator, or until the subject is deemed by the investigator to be lost to follow-up. If, in the opinion of the investigator, it is necessary to monitor a subject beyond the safety follow-up visit, the follow-up period may be extended as necessary. In such instances, the sponsor and the investigator will agree to an acceptable follow-up schedule.

In the event that a subject chooses to withdraw from the study, the investigator should make a reasonable effort to ascertain the reason(s) for withdrawal, while fully respecting the subject's rights. If the subject fails or refuses to return to the study center, an attempt must be made to contact the subject by telephone in order to assess as many safety and efficacy parameters as possible. All data collected over the telephone must be documented and kept in the subject's record.

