14.5. Efficacy Analysis

The following endpoints will be used to evaluate durability of treatment effect:

- Change from baseline in Positive and Negative Syndrome Scale (PANSS) total score and subscales by visit
- Change from baseline in Clinical Global Impression – Severity (CGI-S) by visit
- Time to discontinuation

The PANSS (total and subscale scores) and CGI-S scores, and appropriate changes from baseline, will be summarized using descriptive statistics.

The discontinuation rate will be estimated using the Kaplan-Meier (KM) Method and the KM plot will be provided.

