3. DATA ANALYSIS

3.1. General Statistical Methodology

Baseline for efficacy or safety analysis is defined as the last non-missing assessment before the first dose of ALKS 3831 in the ALK3831-A304 study, and it will be used for all efficacy and safety analysis, unless specified otherwise.

Baseline of precedent study (A303) is defined as the last non-missing assessment before the first dose of study drug in the ALK3831-A303 study. It will be used for the summary of the PANSS total score and subscales and body weight results.

Treatment sequence is defined according to the treatment assignment in antecedent and current studies as ALKS 3831/ALKS 3831 (ALKS 3831 in both ALK3831-A303 study and ALK3831-A304 study) and OLZ/ALKS 3831 (olanzapine in ALK3831-A303 study and ALKS 3831 in

ALK3831-A304 study). All efficacy and safety analysis will be presented by treatment sequence and overall.

In general, descriptive statistics: n, mean, standard deviation (SD), median, minimum, and maximum, for continuous variables and number and percentage of subjects in each category for categorical variables will be provided.

All source data will be presented as subject data listings.

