3.3. Disposition

The number and percentage of subjects completing or prematurely discontinuing the study including reasons for discontinuation will be summarized for the following:

- Subjects who enrolled in the study

- Subjects in the Safety Population
- Subjects who completed the treatment period
- Subjects who discontinued treatment along with reason for discontinuation (as indicated in case report form)

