3.9.1.1. Deaths, Serious and Other Significant AEs

The number and percentage of subjects who have serious adverse events (SAEs) and AEs leading to premature discontinuation from the treatment will be summarized by system organ class and preferred term.

By-subject listings will be provided for SAEs, AEs leading to treatment discontinuation and AEs leading to death.

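### The Kaplan-Meier analysis of discontinuation due to AE censors non-AE stops, which are competing events, so 1-KM read as a risk is at or above the proportion who actually stop for an AE (minor, cheap to fix)

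*SAP*

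**What the plan says.** SAP 3.8.2 lists time to treatment discontinuation among the endpoints for durability of effect. On the method it says "Time to treatment discontinuation will be analyzed using the Kaplan-Meier method" and "Both all-cause discontinuation and discontinuation due to AE will be summarized". The event time runs from first to last dose for subjects who stop early, for any cause or for an AE depending on the analysis. For everyone else, "Other subjects will be censored at the last dose of the study drug". SAP 3.1 adds "All efficacy and safety analysis will be presented by treatment sequence and overall".

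Protocol 14.5 has only "The discontinuation rate will be estimated using the Kaplan-Meier (KM) Method and the KM plot will be provided", without naming a cause. Protocol 7.3 lists reasons for leaving other than an AE, among them lack of efficacy, loss to follow-up, withdrawal by the subject, protocol deviation, pregnancy and termination by the sponsor.

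AE stops also appear in three other places in the SAP:
- Section 3.3 gives discontinuation by reason, as number and percentage.
- Section 3.9.1 has an overview table with the number of subjects with AEs leading to treatment discontinuation.
- Section 3.9.1.1 says "AEs leading to premature discontinuation from the treatment will be summarized by system organ class and preferred term", with by-subject listings.

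Neither document mentions competing events or a cumulative incidence function.

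**The concern.** In the AE analysis, the subjects censored at last dose are not only those who completed 52 weeks. They include everyone who stopped for a non-AE reason. Kaplan-Meier treats a censored subject as someone who could still have the event later, but a subject who has stopped study drug cannot later stop it because of an AE. The estimate then describes AE discontinuation in a hypothetical setting where nobody leaves for another reason and censoring is independent. That is a legitimate cause-specific description, but it is not the proportion of enrolled subjects who stop for an AE.

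What is at stake is interpretation. Tolerability is part of the primary objective, and this analysis is the only planned summary of the time course of AE stops. A reader who takes 1-KM as a risk will be at or above the actual proportion. The same report will carry a crude percentage that can be lower, with nothing in the SAP to explain the gap.

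**Working it through.** **Inputs from the documents.** Horizon 52 weeks; N about 540 (SAP 2); the censoring rule in SAP 3.8.2. The documents state no discontinuation rates and no figure to reproduce, so every rate below is an assumption.

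**Direction.** The cumulative incidence adds, at each AE stop, (fraction still on drug) × (AE stops / number at risk). Kaplan-Meier replaces the fraction still on drug by the fraction free of AE stops, which is never smaller. So 1-KM is at or above the cumulative incidence, and strictly above it once any AE stop follows a non-AE stop.

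**Size under constant hazards.** Let a be the true AE proportion at week 52, o the proportion stopping for other reasons, and D = a + o. With 52 weeks as the time unit, λ_AE = −ln(1−D) × a/D, and

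1-KM = 1 − exp(−λ_AE) = 1 − (1−D)^(a/D).

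Example with a = 0.05 and o = 0.30: −ln(0.65) = 0.4308; λ_AE = 0.4308 × 0.05/0.35 = 0.0615; 1-KM = 0.0597.

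| Other discontinuation | 1-KM (true 5%) | Excess × 540, subjects |
|---|---|---|
| 5% | 5.1% | 0.7 |
| 10% | 5.3% | 1.5 |
| 20% | 5.6% | 3.2 |
| 30% | 6.0% | 5.2 |
| 50% | 7.0% | 10.8 |

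For scale, the standard error of a crude 5% is √(0.05 × 0.95/540) = 0.94 points. The excess reaches one standard error only at about 30% other discontinuation.

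At a higher assumed AE proportion the gap is wider: with a = 10% and o = 30%, 1-KM is 12.0%.

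**Before week 52** (a = 5%, o = 30%, f = week/52). 1-KM = 1 − exp(−λ_AE f); cumulative incidence = (a/D)(1 − (1−D)^f).
- Week 26: 3.0% against 2.8%.
- Week 39: 4.5% against 3.9%.
- Week 52: 6.0% against 5.0%.

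**Timing.** Spread other exits evenly over 52 weeks and AE stops evenly over a window. Then 1-KM = 1 − (Y_end/Y_start)^p, where Y is the fraction on drug at the two ends of the window and p is the AE share of exits within it.
- AE stops in weeks 0-8, o = 50%: Y goes from 1 to 1 − 0.05 − 0.5 × 8/52 = 0.873; p = 0.05/0.127 = 0.394; 1-KM = 5.2%. Over o = 5% to 50% the range is 5.0% to 5.2%.
- AE stops in weeks 26-52, o = 50%: Y goes from 0.75 to 0.45; p = 0.05/0.30; 1-KM = 8.2%. Over o = 5% to 50% the range is 5.2% to 8.2%.

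**Simulation check.** In 900 simulated trials with N = 540 (three assumed rate pairs), 1-KM was at or above the Aalen-Johansen estimate every time. Nobody was censored before day 364 in these runs, and Aalen-Johansen equalled the crude AE proportion. At a = 6%, o = 30% the means were 7.2% for 1-KM and 6.0% for Aalen-Johansen.

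**What the alternative does between sequences.** Take the same on-drug AE hazard in both sequences, λ_AE = −ln(0.74) × 0.06/0.26 = 0.0695. Let other discontinuation be 20% in one and 40% in the other. 1-KM is 6.7% in both. The cumulative incidence is 6.0% and 5.2%.

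**The case against.** The strongest reply is that the error depends on a reading the SAP does not make. SAP 3.8.2 promises no AE-specific percentage and no statement of risk, and mock outputs are in a separate document (SAP 9), where labels may be set. The endpoint is listed under durability of effect, while AE discontinuation as a safety outcome is tabulated by crude incidence, which is unaffected. No test or interim decision uses the curve. The gap is small under many assumptions. The 540 is an estimated maximum, and results are also shown by sequence: with 270 per sequence (an assumption) the standard error of a crude 5% is 1.33 points, and the excess reaches it only at about 38% other discontinuation. Finally, a cause-specific Kaplan-Meier curve is a fair on-drug summary, and the equal-hazard example shows that it compares sequences more cleanly than the cumulative incidence does.

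Most of this stands and sets the grade of the point. It does not remove it: the censoring rule is explicit, nothing in either document labels the estimate as cause-specific, and the estimand argument is met by keeping the curve under that label.

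Three stronger readings are tempting, and the documents do not support them:
- A reader might infer that an inflated week-52 AE discontinuation rate will be reported. No such figure, and no AE-specific plot, is explicitly promised; the rate and plot in Protocol 14.5 name no cause.
- A reader might infer that this is the only planned output on when AE stops occur. By-subject listings are planned in SAP 3.9.1.1. Their columns are not described, so they may show timing; the Kaplan-Meier analysis is the only planned summary of it.
- A reader might extend the point to the all-cause analysis. There every early stop is an event, so no competing exit of this kind is censored.

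**Conclusion.** The point holds as a minor one. The planned AE-specific Kaplan-Meier analysis censors competing exits, so 1-KM must not be read as the proportion of subjects who stop for an AE; it is at or above that proportion. With an assumed true 5% and constant hazards, the overstatement is 0.1 to 2.0 points for 5% to 50% other discontinuation. It is about 0.2 points at most if AE stops come in the first 8 weeks, and up to 3.2 points if they all come in the second half of the year. These sizes rest wholly on assumed rates and timing.

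No test is affected, and the end-of-study count or percentage of AE stops is already planned in SAP 3.3, 3.9.1 and 3.9.1.1. What lacks a correct summary is the time course before week 52.

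**What to change.** Amend SAP 3.8.2 as follows:
- Keep Kaplan-Meier for all-cause discontinuation.
- For discontinuation due to AE, report the Aalen-Johansen cumulative incidence by treatment sequence and overall. Treat non-AE discontinuation as the competing event, and censor completers and administrative ends such as termination by the sponsor.
- If the AE Kaplan-Meier curve is kept, label it cause-specific (hypothetical, assuming independent censoring) and do not describe it as a risk.
- State that the cumulative incidence also depends on non-AE dropout, so a difference between sequences must not be read as a difference in AE hazard while on drug. This is the main downside of the change.

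The cost is one sentence each for the estimator, the label and the interpretation, plus a standard procedure option; no new data are needed. At week 52 the new estimate will closely match the planned crude percentage, exactly only if nobody is censored before then, so the gain is a correct curve up to that point.

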3.8.3. Other Endpoints

- Change from baseline in IWQOL-Lite scales (total score, physical function, self-esteem, sexual life, public distress, and work) by visit
- Change from baseline in EQ-5D-5L index value and visual analogue scale (VAS) score by visit

Descriptive statistics of IWQOL-Lite scales and EQ-5D-5L, including n, mean, SD, median, minimum, and maximum, will be summarized by visit based on observed data.

The IWQOL-Lite scale is a 31-item self-report measure of obesity-specific quality of life. IWQOL-Lite provides an overall total score as well as scores on five domains: (1) physical function, (2) self-esteem, (3) sexual life, (4) public distress, and (5) work. The raw scores will be transformed as follows (Tessier et al, 2012)³: the transformed scores range from 0 to 100, with 100 representing the best, and 0 representing the most impaired quality of life.

$$Transformed\ Score = \frac{maximum\ theoretical\ score - actual\ score}{test\ score\ range} \times 100$$

The EQ-5D-5L is a validated quality of life questionnaire developed by the EuroQol Group in order to provide a simple, generic utility measure for characterizing current health states of patients. EQ-5D-5L is designed for self-completion by subjects. It consists of 2 parts – the EQ-5D-5L descriptive system and the VAS.

The EQ-5D-5L descriptive system comprises 5 dimensions: mobility, self-care, usual activities, pain/discomfort, and anxiety/depression. Each dimension has 5 levels.

The 5 dimensional 5-level systems are converted into an index value. Values for theoretically possible health states are calculated using a regression model and weighted according to the social preferences of the U.S. population (Van Hout et al, 2012)⁴. The VAS records the respondent's self-rated health on a vertical VAS. The VAS has 100 (Best health you can imagine) at the top, and 0 (Worst health you can imagine) at the bottom. This information can be used as a quantitative measure of health outcomes as judged by the individual respondents. EQ-5D-5L self-reported VAS data generates information on the self-perceived overall health-related quality of life. Change from baseline in EQ-5D-5L index value and VAS score will be analyzed.

3.8.4. Multiple Comparison / Multiplicity

Not applicable.

3.9. Safety Analysis

3.9.1. Adverse Events

Incidence of treatment emergent AEs (TEAEs) will be analyzed as a safety endpoint. Adverse events will be coded by System Organ Class and Preferred Term using the Medical Dictionary for Regulatory Activities (MedDRA[®]) Version 21.0 or higher. The verbatim term will be included in the AE listings.

An AE (coded by preferred term) will be considered as a TEAE if the event is newly occurring or worsening on or after the date of first dose of study drug and within 7 days after the last dose of study drug in this study.

An overview table, including number of subjects with TEAEs, AEs leading to treatment discontinuation, study drug related TEAEs, and SAEs will be provided.

The incidence (number and percentage) of subjects reporting TEAEs during the treatment period will be presented for the following categories:

- System organ class and preferred term
- Preferred term, and including the following subset:
 - TEAEs experienced by $\geq 2\%$ of subjects (in any group)
- System organ class, preferred term, and severity
- System organ class, preferred term for severe TEAEs

- System organ class, preferred term, and relationship
- System organ class, preferred term for study drug related TEAEs

If the same preferred term occurred more than once for the same subject, the subject will be counted only once for that preferred term using the most severe and most related occurrence for the summarization by severity and by relationship to the study drug.

In addition, the number and percentage of subjects reporting AEs during the safety follow-up period will be tabulated by the system organ class and preferred term.

Subgroup analysis by age (<40 years vs \geq 40 years), sex (Female vs Male) and race (Black or African American, White, and Other) will be performed for TEAEs during the treatment period by preferred term.

3.9.1.1. Deaths, Serious and Other Significant AEs

The number and percentage of subjects who have serious adverse events (SAEs) and AEs leading to premature discontinuation from the treatment will be summarized by system organ class and preferred term.

By-subject listings will be provided for SAEs, AEs leading to treatment discontinuation and AEs leading to death.

3.9.1.2. Other Significant AEs

In addition, incidence of a selected subset of relevant AEs in this class of drugs (e.g., Extrapyramidal symptoms [EPS) TEAEs, TEAE to evaluate potential of suicidal ideation and behavior, etc.) will be summarized by preferred term. The selection of AEs per subset will be based on the preferred terms from Standardized MedDRA queries (SMQs) or Customized MedDRA queries (CMQ's).

3.9.1.3. Analysis of Abuse Potential, Withdrawal, and Dependence

3.9.1.3.1. Analysis of Abuse Potential

Number and percentage subjects with TEAEs to evaluate abuse potential will be summarized by category (abuse behavior, euphoria related, and non-specific) and preferred term. The selection of AEs per subset will be based on the preferred terms from Customized MedDRA queries (CMQs).

3.9.1.3.2. Analysis of Withdrawal and Dependence

Adverse events with an onset date within 2 weeks (>2 to ≤ 16 days) after the last dose of the study drug in those subjects who have received at least 4 weeks of study drug will be included in the evaluation of the potential for withdrawal and dependence. The selection of AEs per subset will be based on the preferred terms from Customized MedDRA queries (CMQs).

The number and percentage of subjects with such AEs will be summarized in the Post-discontinuation Safety Populations by preferred term for subjects with a duration of study drug exposure ≥ 4 weeks.

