7. SELECTION AND WITHDRAWAL OF SUBJECTS

7.1. Subject Inclusion Criteria

Each subject must meet all of the following inclusion criteria to be qualified to participate in this study.

1. Subject is willing and able to provide informed consent; subject has signed the informed consent form before initiation of any study specific procedures
2. Subject agrees to use an acceptable method of contraception for the duration of the study (please refer to [Section 8.4.1](#) for additional details regarding contraception)
3. Subject is willing and able to follow the study procedures as outlined in the protocol
4. Subject has the potential to benefit from the administration of ALKS 3831, in the opinion of the investigator
5. Subject has completed the 24-week treatment period in the antecedent study [ALK3831-A303](#) within 7 days

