3.2.3. Post-discontinuation Safety Population

Post-discontinuation Safety Population will be defined as subjects in the Safety Population and met any of the following criteria:

- Completed at least one follow-up visit after >2 day within 16 days of the last dose of ALKS 3831
- Reported at least one AE reported after >2 day after the last dose of ALKS 3831

AE to evaluate potential for drug withdrawal and dependence emerging following discontinuation of ALKS 3831 will be assessed for this population, during the period of >2 days to 16 days after the last dose of drug for subjects with at least 4 weeks study drug exposure.

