3.7.2. Extent of Exposure to Study Drug

Duration of exposure to study drug (ALKS 3831) is defined as the number of days from the date of the first dose of study drug of this study (ALK3831-A304) to the date of the last dose of study drug, inclusive (ie, last dose date – first dose date + 1 day). Duration of study drug administration will be summarized.

The overall mean and modal dose of olanzapine will be summarized

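### The 4-week exposure minimum for the withdrawal and dependence table, counted from the first A304 dose, leaves out early stoppers who already have about 24 weeks or more of ALKS 3831

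*SAP*

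**What the plan says.** SAP 3.9.1.3.2 takes adverse events starting more than 2 and up to 16 days after the last dose, "in those subjects who have received at least 4 weeks of study drug". It tabulates them "by preferred term for subjects with a duration of study drug exposure" of at least 4 weeks. SAP 3.2.3, which defines the Post-discontinuation Safety Population, repeats that the assessment is "for subjects with at least 4 weeks study drug exposure". The two bullets that define membership of that population carry no exposure limit.

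SAP 3.7.2 is the only place where exposure duration is defined. It counts days "from the date of the first dose of study drug of this study (ALK3831-A304") to the last dose, inclusive.

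SAP 3.1 sets up two treatment sequences for all summaries. One of them took "ALKS 3831 in both ALK3831-A303 study and ALK3831-A304 study"; the other took olanzapine in A303 and ALKS 3831 only in A304.

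Protocol 7.1 makes it an entry condition that the "Subject has completed the 24-week treatment period in the antecedent study" ALK3831-A303 within 7 days. Footnote b to Protocol Table 3 allows A304 Visit 1 on the same day as the last A303 treatment visit.

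**The concern.** A minimum exposure in a withdrawal analysis presumably ensures that a subject has taken the drug long enough for stopping it to be informative. The SAP does not state its reason, so this purpose is inferred. For OLZ/ALKS 3831 an A304 clock does the job, because samidorphan starts in A304. For ALKS 3831/ALKS 3831 it does not: these subjects arrive with a completed 24-week treatment period on the same product, yet their clock restarts at zero.

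The table can only be informed by people who stop the drug. Completers who move to ALK3831-A308 continue ALKS 3831 and need no follow-up visits (Protocol 8.1; Table 3, footnote c). The table therefore rests on early discontinuers and on completers who do not roll over, and early stoppers are likely to be a larger share of that set than of all 540. At stake is the completeness of a prespecified safety table, not the trial's main conclusions.

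**Working it through.** There is no sample size or power figure to reproduce; SAP section 2 says that none was calculated. The check applies the rule in days.

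**Inputs**
- Threshold: 4 weeks = 4 × 7 = 28 days (SAP 3.2.3, 3.9.1.3.2).
- Exposure under the SAP: last A304 dose date − first A304 dose date + 1 (SAP 3.7.2).
- Prior ALKS 3831 in the ALKS 3831/ALKS 3831 sequence: 24 × 7 = 168 days, nominal (Protocol 7.1).
- Gap between studies: 0 to 7 days, not counted as exposure.
- Planned enrolment: about 540, both sequences together (SAP section 2).

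**Rule applied to ALKS 3831/ALKS 3831**, with cumulative exposure = 168 + A304 days:

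| Last A304 dose on day | SAP exposure (days) | In table as written | Cumulative ALKS 3831 | In table if cumulative |
|---|---|---|---|---|
| 1 | 1 | No | 169 days = 24.1 weeks | Yes |
| 14 | 14 | No | 182 days = 26.0 weeks | Yes |
| 27 | 27 | No | 195 days = 27.9 weeks | Yes |
| 28 | 28 | Yes | 196 days = 28.0 weeks | Yes |

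For OLZ/ALKS 3831, ALKS 3831 exposure equals A304 exposure on either definition, so nothing changes.

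**Where the events of an omitted subject go.** The window of more than 2 to 16 days splits at day 7. Events up to 7 days after the last dose meet the TEAE definition in SAP 3.9.1. Events after 7 days fall in the follow-up tabulation (SAP 3.2.2, 3.9.1). All source data are listed (SAP 3.1). None of these outputs isolates the terms of SAP Appendices 4 and 5 within the post-dose window.

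**Possible count.** The documents give neither the split between sequences nor the early discontinuation rate. Assume 40% to 60% of 540 are ALKS 3831/ALKS 3831, and 1% to 10% of those stop within 4 weeks:
- low: 540 × 0.40 × 0.01 = 2.2
- middle: 540 × 0.50 × 0.05 = 13.5
- high: 540 × 0.60 × 0.10 = 32.4

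These are ceilings. To enter the population at all, a subject must also have a follow-up visit in the window or an adverse event more than 2 days after the last dose (SAP 3.2.3). Early stoppers with neither are outside the table under any exposure rule.

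**The case against.** The strongest objection is that the A304 clock is inferred. Neither 3.2.3 nor 3.9.1.3.2 cites 3.7.2 or ties the 4 weeks to A304, although the SAP does add the study number elsewhere, for example in 3.6. This stands as a caveat, but it does not rescue the text. The only definition of exposure duration is the A304 one, and a programmer would use it. If cumulative exposure was meant, the SAP does not say so. It also leaves open whether A303 olanzapine would count: 3.7.2 equates study drug with ALKS 3831, while 3.1 speaks of study drug in A303 for both arms.

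Several stronger readings are tempting, and the documents do not support them:

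- A reader might infer that the rule discards the longest-exposed subjects. It drops the shortest-exposed members of their sequence, at 24.1 to 27.9 weeks. Those retained have 28.0 weeks or more, up to 24 + 52 = 76 weeks.
- A reader might infer that the events vanish, or that the subjects leave the population. They stay in the Post-discontinuation Safety Population, because its bullets have no exposure limit, and their events are reported elsewhere. Whether the percentages use the whole population or its 4-week subset as denominator is open.
- A reader might infer that 3.7.2 understates exposure by 24 weeks per subject. It openly defines exposure in A304, which matches the A304 baseline and the TEAE start date. That is a legitimate scope choice.
- A reader might infer that the correction makes the two columns comparable. It does not: the effective minimum goes from about 28 against 4 weeks to about 24 against 4. The case rests on who meets the purpose of the minimum, not on comparability.

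**Conclusion.** The point holds in a limited form. On the SAP's own definition, ALKS 3831/ALKS 3831 subjects whose last A304 dose falls on Days 1 to 27 are left out of the withdrawal and dependence table, although each already has about 24 weeks or more of nearly continuous ALKS 3831. A stated rule gives an exclusion that its evident purpose does not call for.

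The effect is confined to early stoppers in one sequence and one descriptive table. The number cannot be derived; about 2 to 32 is an assumed ceiling, and the true figure is probably small. The direction of any bias is unknown.

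The conclusion rests on two assumptions: that 3.7.2 supplies the clock for the 4-week criterion, and that a completed A303 treatment period means roughly 168 days of dosing. Visit windows or missed doses could bring the second slightly below 24 weeks, but nowhere near 4.

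**What to change.** In SAP 3.2.3 and 3.9.1.3.2:
- State that the 4-week criterion uses cumulative ALKS 3831 exposure for ALKS 3831/ALKS 3831: the A303 duration plus the A304 duration, without the gap between them.
- State that it uses A304 exposure for OLZ/ALKS 3831, so that A303 olanzapine does not count.
- Apply the same criterion to numerator and denominator, and name the denominator.

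SAP 3.7.2 need not change. A cumulative ALKS 3831 duration line for the ALKS 3831/ALKS 3831 sequence is optional.

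The cost is a few lines of SAP wording and one derived variable. The SAP already relies on A303 treatment assignment and on an A303 baseline set by the first A303 dose (3.1), so the only further input is the last A303 dose date. Nothing changes in study conduct, and no new data are collected.
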